4.1.1 Titration procedure

The dose of AZD1656 will be individually titrated stepwise provided that the glucose values of the subject are within acceptable limits. The decision to increase the dose on study Day 2 (dose titration) and the decision to continue on the individual tolerated dose on study Day 3-4 will be based on the morning fasting glucose on the actual day and the post-prandial glucose values from the previous day ([Figure 2](#)). After Day 2 no further dose increases are allowed, but down-titration to 40 mg bid may be needed. Study specific discontinuation criteria applies for hypoglycaemia or pronounced hyperglycaemia as described in [Section 5.4.3](#).

4.1.2 Rescue treatment – Low plasma glucose outside titration period

The following section applies during the residential period of the study (Visit 3), excluding 0-6 hours post dosing with AZD1656 on study Day 5 and 8.

If the subject experiences hypoglycaemic symptoms, a plasma glucose measurement should be obtained (before any treatment) and the subject should be treated according to local practice. For subjects with hypoglycaemia, defined as P Glucose <2.5 mmol/L (45 mg/dL), approximately 25 g glucose (juice) orally should be given as rescue treatment. Intravenous glucose could also be considered according to the judgement of the investigator.

If recurrent hypoglycaemia (defined as P-Glucose <2.5 mmol/L [45 mg/dL]), or hypoglycaemia that is difficult to cure, the subject should be discontinued from the study, Section 5.4.3.

If rescue treatment is needed during titration of investigational product (IP), the dose of AZD1656 should be reduced, see Figure 2. If rescue treatment is needed already after the initial dose the subject should be discontinued from the study.

Figure 1 Study design

[figure not shown]
[figure not shown]

Figure 2 Dose titration and glucose value

Note: the titration period is limited to Day 1 and Day 2 for each subject. On Day 3 the dose will be kept or reduced if needed.

Figure 3 Overview step wise hypoglycaemic clamp

[figure not shown]

Table 1 Study plan

| Event | Enrolment | Metfor- min treatment | Titration period | Maintenance period | Hypo- glycemic Clamp period 1 | Recovery period | Hypo- glycemic Clamp period 2 | Follow- up |
|--|--|-----------------------------|---------------------|-----------------------|--|--------------------|--|----------------------------------|
| Visit | 1 | 2 | 3 | 3 | 3 | 3 | 3 | 4 |
| Study Day | ≤28 days before rando- misation | Day -8 | D1-D2 | D3-D4 | D 5 | D 6-7 | D 8 | 7-10 days after Visit 3 |
| Informed consent | X | | | | | | | |
| Inclusion/exclusion criteria | X | | | | X | | | |
| Medical and surgical history including T2DM history | X | | | | | | | |
| Physical examination | X | | | | | | | X |
| Ophtamologic examination ^a | X | | | | | | | |
| Laboratory screening | X ^b | | X ^c | | X ^c | X ^c | X ^c | X |
| C-peptide, HbA1c & GAD antibodies | X | | | | | | | |

| Event | Enrolment | Metfor- min treatment | Titration period | Maintenance period | Hypo- glycemic Clamp period 1 | Recovery period | Hypo- glycemic Clamp period 2 | Follow- up |
|---|--|-----------------------------|---------------------|-----------------------|--|--------------------|--|----------------------------------|
| Visit | 1 | 2 | 3 | 3 | 3 | 3 | 3 | 4 |
| Study Day | ≤28 days before rando- misation | Day -8 | D1-D2 | D3-D4 | D 5 | D 6-7 | D 8 | 7-10 days after Visit 3 |
| Body weight/height ^d | X | | | | | | | X |
| Drug screen test | X | | | | | | | |
| Change to clinic provided Metformin treatment | | X | | | | | | |
| Arrival at clinic | | | X | | | | | |
| Randomisation | | | | | X | | | |
| 7-point glucose (bedside) | | X ^c | X | X | | X | | |
| 24 h glucose ^f | | | | | X | | X | |
| ECG/BP/pulse | X | | X ^g | X ^g | X ^g | X ^g | X ^g | X |
| Genetic blood sample (optional) | | | | | X | | | |
| Telemetry | | | | | X | | X | |
| Administration of IP | | | X | X | X | X | X | |
| Standardised meals | | | X | X | | X | | |
| Hypoglycemic clamp | | | | | X | | X | |
| PK/PD/CR blood sampling | | | | | X ^h | | X ^h | |
| AE recording ⁱ | X | X | X | X | X | X | X | X |

^a Excluded for subjects who have done such examination within 3 months from study start.

^b Also includes HIV, Hepatitis B and C test and for women FSH unless age >50 years and 2 years without menstruation periods.

^c Laboratory screening will be done pre dose on Day 1, 5, 6, 8 and morning day 9 (24 hours after last dose).

^d Height only measured at Visit 1.

^e Only morning sample.

^f Time points specified in [Table 2](#).

^g ECG, BP and pulse will be recorded pre dose on Day 1, 4 and 7 and pre dose and 12 h post dose on Day 5 and Day 8 (see [Table 2](#)).

^h PK, PD and CR blood sampling will be done repeatedly during the 24-hour period after dose (see [Table 2](#)).

ⁱ Adverse Events will be collected from the time when informed consent is obtained until the end of the study (including the follow-up visit). Before the time of the first administration of investigational product only serious adverse events need to be collected.

Table 2 Time schedule during Day 5 and Day 8

| Protocol Time | CR/PD | ECG/ BP/ Pulse | Safety lab screen | 24 h Glucose (bedside) | PK | Other |
|---------------|-------|----------------------|-------------------------|---------------------------|----|---|
| Pre-dose | X | X | X | X | | Start telemetry |
| 0000 | | | | | | Adm of IP and start Clamp (Biostator) |
| 0015 | | | | X | 1 | |
| 0030 | | | | X | 2 | |
| 0045 | | | | X | | |
| 0100 | X | | | X | 3 | |
| 0130 | X | | | X | 4 | |
| 0200 | X | | | X | 5 | |
| 0230 | X | | | X | | |
| 0245 | X | | | | | |
| 0300 | X | | | X | | Clamp release and Glucagon injection |
| 0315 | | | | X | | |
| 0320 | | | | X | | |
| 0330 | X | | | X | | |
| 0345 | | | | X | | |
| 0400 | X | | | X | 6 | Reversed clamp ^a |
| 0430 | X | | | X | | Meal ^b |
| 0500 | X | | | X | | Normalised P-glucose ^c |
| 0600 | X | | | X | | Stop telemetry |
| 1200 | | X | | | 7 | |
| 2400 | | | | X | 8 | |

- a Minimal Plasma glucose value increased from 2.7 to 3.2 mmol/L.
b Minimal plasma glucose value increased from 3.2 to 4.0 mmol/L.
c Minimal plasma glucose value increased from 4.0 to ≥ 5.0 mmol/L.

Table 3 Time schedule during Day 1, 2, 3, 4, 6, 7 and 9^a

| Protocol Time | Glucose sampling (bedside) | ECG/ BP/ Pulse | Safety lab screen | Other |
|---------------|----------------------------|----------------|-------------------|---------------------------------|
| Pre-dose | X | X ^b | X ^c | |
| 0000 | | | | Adm of IP followed by breakfast |
| 0200 | X | | | Snacks |
| 0400 | X | | | Lunch |
| 0600 | X | | | Snacks |
| 0900 | X | | | Adm of IP followed by dinner |
| 1200 | X | | | Evening meal |
| 1400 | X | | | At bedtime |

^a Day 9 only includes pre dose safety lab screen and one glucose sampling after breakfast, thereafter discharge from clinic.

^b Only on Day 1, 4 and 7

^c Only on Day 1, 6 and 9

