Type 1 and 2 diabetic patients with severe hypoglycemia are treated with glucose injections or intra muscular injections with the pancreas hormone glucagon. The latter treatment is crucial for out of hospital events and is often used by bystanders (relatives) as the first treatment when the patient is unconscious. Glucagon acts quickly on the liver and converts stored glycogen into glucose which subsequently is released into the bloodstream. A GKA may interfere with this process due to its effect on liver by increasing available glucose 6-phosphate and thereby the substrate for glycogen production.

Preliminary data from the global SAD (D1020C00001) and MAD (D1020C00002) studies have demonstrated that AZD1656 is rapidly absorbed and maximum concentration (C_{max}) is reached within 1 hour. The compound is rapidly eliminated with a half-life ($t_{1/2}$) of approximately 3-4 hours. AZD1656 is metabolised to the active metabolite AZD12555623. The mean exposure to the metabolite is approximately 20% compared to AZD1656. The C_{max} of the metabolite is reached at the same time as for the parent compound. The initial AZD12555623 decline is parallel to AZD1656 decline but a slower terminal elimination phase is evident. In rats, the exposure to the active metabolite AZD12555623 is approximately 2 fold higher compared to the exposure to AZD1656.

AZ intends to perform genetic research in the AZD1656 clinical development programme to explore how genetic variations may affect the clinical parameters associated with AZD1656.

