2.4 Benefit/risk and ethical assessment

The subjects will be hospitalised during the study in order to carefully monitor glucose levels, achieve maximal tolerated dose of AZD1656 given twice-daily (bid) and avoiding spontaneous hypoglycaemia.

The dose will be titrated over two days up to the maximal tolerated dose, where it will be maintained for another two days. Giving the maximally tolerated bid dose of AZD1656 as a single dose after an overnight fast will induce hypoglycaemia in both treatment arms (Day 5 and Day 8). Insulin may be needed as a supplement in order to achieve stable glucose levels during these study days.

A glycaemic clamp with a continuously titrated glucose and/or insulin infusion (via an automated glucose clamp device, Biostator[®]) will be used to allow a controlled step-wise lowering of plasma glucose, and the plasma glucose level will not be allowed to be lower than 2.7 mmol/L

The recovery of plasma glucose will be measured with and without intramuscular glucagon. The Biostator[®] will also be used to guarantee a safe recovery of the plasma glucose levels.

In the ongoing SAD study (D1020C00001), single doses up to 180 mg AZD1656 have been given to healthy volunteers during euglycemic clamp and in the ongoing MAD study (D1020C00002) multiple oral doses of up to 80 mg AZD1656 have been given bid to patients with T2DM. These ongoing studies have not raised any safety concern.

All of the significant adverse findings seen in the toxicology studies are considered to be secondary to hypoglycaemia and/or relatively minor, reversible or can be monitored in clinical studies.

Careful monitoring regarding symptoms or laboratory abnormalities indicative of any adverse effects, including muscle symptoms, creatinekinase (CK) and aspartataminotransferas (AST) will be observed during the entire study.

Blood samples for deoxyribonucleic acid (DNA) extraction will be taken (optional) and DNA will be saved for potential future research into genes that may influence response to AZD1656.

There are no direct benefits for the subjects participating in this study.

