administered intra muscular or a spontaneous recovery in glucose levels will be awaited. After the release of the hypoglycaemic clamp, the Biostator[®] will continue to follow glucose on a minute by minute basis at least until two consecutive plasma glucose values are obtained at or above 5.0 mmol/L without concomitant glucose infusion. The Biostator's glucose analyzer will be re-calibrated in regular intervals by means of a YSI STAT2300 glucose analyzer throughout the clamp procedure, at least every 10-15 minutes.

Ninety minutes past clamp release (4.5 h post dose), the subjects will be served a meal with food ad libitum. Plasma glucose, counter regulatory hormones and pharmacodynamic (PD) markers will be followed for 3 hours after the clamp release (6 h post dose).

In order to avoid prolonged hypoglycaemia, a reversed clamp will be applied at 240 minutes post dosing with AZD1656. A glucose infusion will be used as needed to achieve a minimum plasma glucose level of 3.2 mmol/L at 240-270 min, 4.0 mmol/L at 270-300 min and ≥ 5.0 mmol/L after 300 min post dosing with AZD1656. The Biostator[®] will be disconnected at 360 min post dosing with AZD1656 provided that two consecutive plasma glucose values of at least 5.0 mmol/L are measured without ongoing glucose infusion. Plasma glucose values will be monitored also during the recovery period, Day 6-7, and in the morning on the day of discharge (Day 9), see [Table 4](#).

A pre-entry visit will take place within 28 days before randomisation, Visit 1. If the subjects are eligible to enter the study they will come to the clinic 8 days (Day -8, Visit 2) before Visit 3 to switch to the Metformin provided by the centre and to check their fasting glucose level. The Metformin treatment will be maintained until the end of the residential period, Visit 3. A follow-up visit (Visit 4) will take place 7-10 days after Visit 3.

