6.4.2 Doses and treatment regimens

The Metformin treatment will be provided by the site 8 days before subjects start the treatment with AZD1656 (Visit 3). All subjects will be given the same generic commercial Metformin immediate release formulation (major brand). Commercial Metformin in original packages will be purchased locally by the Clinical Research Organisation (CRO) and will be labelled by the study site personnel.

The Metformin will be administered once or twice daily with the first dose in the morning. If the subject normally takes Metformin more than twice daily, half the total daily dose will be administered bid, with the first dose in the morning and the second dose in the evening. If the subject normally takes Metformin once daily the total daily dose will be administered in the morning.

The Metformin dose should be taken after IP in the morning (before breakfast) and, if applicable, before dinner (9 hours later), after the second daily dose of IP.

At Visit 3, Day 1, all subjects will start their AZD1656 treatment with a titration period where they will receive oral solution of AZD1656 40 mg bid for one day on top of their Metformin treatment. Day 2 they will receive 80 mg bid, and, if tolerated, continue with that dose for another 2 days or, if not tolerated, maintain the dose of 40 mg bid for another 2 days. On Day 5 each subject will be randomised to the two treatment regimens AB or BA in random order. On Day 5 and Day 8 the AZD1656 dose, the total daily dose of 80 mg or 160 mg, will be given as a single dose in the morning after an overnight fast.

The suspension will be administered with the subjects in an upright position and the container will be rinsed with 2x30 mL of tap water to collect the remainings of the study drug in the container. The subjects will then drink an extra glass (150 mL) of tap water.

The A treatment includes an intra muscular injection of 1 mg glucagon at 3 hours post dose. Glucagon will be purchased locally in commercially available packages by the CRO, and will be labelled by the study personnel.

During Day 6-7 the subjects will receive the same dose of AZD1656 oral solution bid as on Day 3 and 4.

Insulin solution for intravenous use during the Hypoglycemic Clamp will be locally purchased by the CRO, Profil.

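### On the two clamp days no glucose reading is scheduled from 6 h to 24 h after the full single dose, although ordinary days have readings at 9, 12 and 14 h

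*Protocol*

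**What the plan says.** **Dose.** On Days 5 and 8 the total daily dose "will be given as a single dose in the morning after an overnight fast" (Section 6.4.2). No evening AZD1656 dose is planned on those days.

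**Clamp-day glucose.** Table 2 lists the times under the column "24 h Glucose (bedside"). The last mark before the gap is at 0600 and the next is at 2400. The 1200 row has ECG, blood pressure, pulse and a PK sample, but no glucose. Table 1 does not apply the 7-point glucose profile on Days 5 and 8.

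**Device.** Section 4.1 sets the condition for taking the clamp device off: "disconnected at 360 min post dosing with AZD1656 provided that two consecutive plasma glucose values of at least 5.0 mmol/L are measured". Any infusion of glucose must have stopped by then.

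**After 6 h.** Section 4.1.2 excludes the first 6 h on these two days and governs the rest: "If the subject experiences hypoglycaemic symptoms, a plasma glucose measurement should be obtained".

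**Ordinary days.** Table 3 has glucose at 9, 12 and 14 h. Two of those rows read "0900 | X | | | Adm of IP followed by dinner" and "1400 | X | | | At bedtime".

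**Stated purpose.** Section 2.4: "The subjects will be hospitalised during the study in order to carefully monitor glucose levels". The same sentence adds avoiding spontaneous hypoglycaemia. The synopsis lists plasma glucose among the safety outcomes.

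**The concern.** The two days with the largest single dose have the sparsest glucose schedule once the device is off. Section 2.4 describes patient experience only up to 80 mg twice daily. Single doses up to 180 mg were given to healthy volunteers under a euglycaemic clamp. So the hours after disconnection on Days 5 and 8 are less well supported by earlier patient data than the hours after an ordinary dose.

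Between 6 h and 24 h the protocol looks for a low value only when the subject reports symptoms, so a low value without symptoms would go unrecorded. The rule in Section 5.4.3, which counts values below 2.5 mmol/L on two occasions, can act only on measurements that are taken. The only clamp-day food that the protocol times is the meal at 4.5 h. Ordinary days schedule snacks at 6 h, dinner at 9 h and an evening meal at 12 h.

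What is at stake is safety information and subject protection. The primary variable is read 20 minutes after clamp release, the recovery times fall within the clamp session, and PK sampling has its own 12 h and 24 h draws. None of these depends on the missing readings.

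**Working it through.** **Step 1: is the gap real, or lost in reading the table?** Glucose marks in Table 2: pre-dose; 0015, 0030, 0045, 0100, 0130, 0200, 0230, 0300, 0315, 0320, 0330, 0345, 0400, 0430, 0500, 0600; and 2400. That is 1 + 16 + 1 = 18. Over two days this gives 18 × 2 = 36 samples, and 36 × 0.5 mL = 18 mL. Table 4 states 18x2=36 and 18 mL, so the count is reproduced. The Table 4 rows sum to the stated 467.8 mL. The CR/PD column, which also yields plasma glucose, has 12 marks, the last at 0600, matching 12x2=24 in Table 4.

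**Step 2: longest interval between scheduled readings.**
- Days 5 and 8: 24 − 6 = 18 h, with no reading in between.
- Ordinary days: readings at 9, 12 and 14 h, then the next morning before dosing; 24 − 14 = 10 h.

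**Step 3: how much drug is present in the gap?** Inputs from Section 2.1: peak within 1 h (taken as 1 h) and half-life h of 3–4 h. Assumptions: dose proportionality, parent drug only, no carry-over from the previous evening. The unit is the peak after one twice-daily dose.
- Clamp day: 2 × 2^(−(t−1)/h)
- Ordinary day: 2^(−(t−1)/h), plus 2^(−(t−10)/h) from t = 10 (second dose at 9 h)

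| Hours after dose | Clamp day (h=3 to h=4) | Ordinary day (h=3 to h=4) |
|---|---|---|
| 6 | 0.63–0.84 | 0.31–0.42 |
| 8 | 0.40–0.59 | 0.20–0.30 |
| 9 | 0.31–0.50 | 0.16–0.25 |
| 12 | 0.16–0.30 | 0.71–0.86 |
| 14 | 0.10–0.21 | 0.45–0.61 |

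Until the ordinary-day second dose, clamp-day exposure is twice the ordinary-day level. From 12 h it is well below.

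A useful benchmark is the ordinary-day level at 14 h, because the protocol already accepts 10 h without a reading from there. At 6 h the clamp day stands at 0.630/0.446 = 1.41 times that level (h=3) or 0.841/0.605 = 1.39 times (h=4). It falls below the benchmark at 1 + h × log2(2/level at 14 h), which is 7.49 h (h=3) or 7.90 h (h=4).

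**Step 4: what would added readings do?**
- One reading at 8 h: the longest interval becomes 24 − 8 = 16 h.
- Readings at 9, 12 and 14 h: the longest interval becomes 24 − 14 = 10 h, equal to ordinary days.

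**The case against.** The strongest reply is that this is a monitoring choice and not an error. Tables 1, 2 and 4 agree with each other, and no rule in the protocol requires a reading between 6 h and 24 h. That stands: there is no contradiction, and the 24 h in the column heading is no promise of even coverage, since Table 1 refers to Table 2 for the times.

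The risk is also largely handled. Insulin stops at 180 min, a meal is served at 4.5 h, and glucose infusion supports at least 5.0 mmol/L after 300 min. A subject who cannot reach two consecutive values of 5.0 mmol/L without infusion stays on the device. Subjects are in-house, unscheduled readings are possible, and the ordinary-day 9, 12 and 14 h readings accompany a second dose that clamp days lack. Modelled exposure at 6 h on a clamp day (0.63–0.84) is no higher than at 2 h on an ordinary day: 2^(−1/3) = 0.79 for h=3 and 2^(−1/4) = 0.84 for h=4. All of this stands and keeps the severity low. It does not cover a low value without symptoms after the device is removed.

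A reader might go further in two directions. One is to treat all 18 h as high risk. The model does not support that, because by 12 h clamp-day exposure is below an ordinary day's. The other is to infer that a single reading at about 8 h would be enough. The documents do not support that either. The protocol defines no period of concern ending near 8 h, the modelled excess over the bedtime benchmark has already ended by 7.5–7.9 h, and 16 h would remain without a reading. For the active metabolite, Section 2.1 says that "a slower terminal elimination phase is evident" without quantifying it.

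**Conclusion.** The gap is real and confirmed by the protocol's own sample count: 18 h without a scheduled glucose reading on each clamp day, against at most 10 h on ordinary days, with only symptom-triggered testing in between. It is a low-severity point about safety monitoring, worth correcting because the correction costs almost nothing and serves the purpose that Section 2.4 gives for keeping subjects in hospital. The primary, recovery-time and PK results are unaffected.

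The interval counts need no assumptions beyond the printed tables. The exposure comparison rests on a half-life of 3–4 h, dose proportionality and parent drug only, and it measures exposure, not the chance of hypoglycaemia. It indicates that the early part of the gap matters most. It is not the basis for the proposed times, which simply bring clamp days to the schedule the protocol already uses on ordinary days.

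**What to change.** In Table 2, add rows at 0900 and 1400 with a bedside glucose mark, and mark glucose on the existing 1200 row, where staff already take the PK sample, ECG and vital signs.

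In Table 4, change the 24 h glucose row to 21x2=42 samples and 42 × 0.5 = 21 mL, and the total to 467.8 − 18 + 21 = 470.8 mL.

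A further reading at 7–8 h is optional. If it is meant to fall within the modelled excess, it belongs nearer 7 h, where clamp-day exposure is 2 × 2^(−6/3) = 0.50 (h=3) or 2 × 2^(−6/4) = 0.71 (h=4), still above the benchmark of 0.45 or 0.61. It would add 1 mL per subject.

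The cost of the main change is three 0.5 mL bedside samples per clamp day, 3 mL per subject in all, in subjects already in-house, plus two table edits. There is no real trade-off.

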4.1 Overall study design and flow chart

In total, 10 T2DM patients treated with Metformin, aged ≥ 18 to ≤ 75 years, will participate in the study to ensure 8 evaluable patients, hereafter called subjects.

The total study period is approximately 4-8 weeks and includes four visits to the clinic, see [Figure 1](#).

Visit 3, treatment/residential period

Each subject will enter a titration phase of two days, with 7-point plasma glucose monitoring, starting at 40 mg bid for one day and increased to 80 mg bid, if tolerated, the second day. Thereafter the tolerated dose, 40 or 80 mg bid, will be maintained for two more days.

The subjects will then (Day 5) be randomised to one of two treatment arms in a cross-over manner, where the full daily oral dose of AZD1656 will be given in the morning under fasting condition to induce hypoglycaemia. The treatment sequence will be given in the randomisation list. The single dose will be followed by either a subsequent injection of glucagon or spontaneous recovery from hypoglycaemia by the CR response depending on treatment arm.

After a recovery phase of two days (Day 6 and 7) where AZD1656 will be maintained at the same dose bid as Day 3-4, subjects will be subjected to a new period of controlled hypoglycaemia followed by alternate treatment as to the previous hypoglycaemic study period, see [Figure 1](#).

On Day 5 and 8, after an overnight fast, the full daily dose from Day 3-4 (80 mg or 160 mg) will be given as a single oral dose (time 0 min). Blood samples for glucose and hormone analyses will be drawn from a catheter in a cubital vein. Another vein will be used for infusion of insulin and/or glucose, controlled by the Biostator[®], in order to reach glycaemic plateaus of 5 mmol/L (0 to 60 min), 4 mmol/L (60 to 90 min), and 3.2 mmol/L (90 to 150 min). Plasma glucose will then be clamped to a target nadir of 2.7 mmol/L and released at 180 min, ie, insulin infusion will be stopped, see [Figure 3](#).

The fasting state will be maintained 270 min after dosing. Plasma glucose will be followed continuously. When plasma glucose has been clamped aiming at 2.7 mmol/L for 30 minutes (ie, 180 min after dose), the clamp will be released and either 1 mg glucagon will be

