7.8 Health economics (Not applicable)

8. BIOLOGICAL SAMPLING PROCEDURES

8.1 Volume of blood

The total volume of blood that will be drawn from each subject in this study is as follows:

Table 4 Volume of blood to be drawn from each subject

| Assessment | | Sample volume (mL) | No. of samples | Total volume (mL) |
|--|--------------------|---------------------|-----------------|-------------------|
| Safety | Clinical chemistry | 5 mL, V1 and | 5 mL x 1 | 5 |
| | | 3.5 mL, V3&V4 | 3.5 ml x 6 | 21 |
| | Haematology | 3 | 7 | 21 |
| Determination of AZD1656 and its metabolite (AZ12555623) in plasma | | 1.2 | 8x2=16 | 19.2 |
| HbA1c | | Incl in haematology | 1 | 0 |
| Fasting plasma Glucose, V1 | | 2 | 1 | 2 |
| GAD antibodies and C-peptide, V1 | | 3.5 | 1 | 3.5 |
| HIV and hepatitis B and C | | 7 | 1 | 7 |
| INR | | 1.8 | 2 | 3.6 |
| 24h glucose (bedside) | | 0.5 | 18x2=36 | 18 |
| 7-point glucose (bedside) Visit 2 & Visit 3 Day 1, 2, 3, 4, 6, 7 and 9 | | 0.5 | 45 ^a | 22.5 |
| S-insulin and C-peptide (PD) | | Incl in CR | 12x2=24 | 0 |
| GH, Epinephrine, Norepinephrine, glucagons, insulin, cortisol (CR) | | 14 | 12x2=24 | 336 |
| Genotyping (optional) | | 9 | 1 | 9 |
| Total | | | | 467.8 |

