12.2 Calculation or derivation of efficacy variable(s) (Not applicable)

12.3 Calculation or derivation of pharmacokinetic variables

The PK analyses will be performed by Profil. The actual sampling times will be used in the PK calculations. Plasma concentrations below LLOQ will be excluded from the calculations. However, at time points before C_{max} , plasma concentrations below LLOQ will be taken as zero in the calculations.

If data permits, the PK variables of AZD1656 defined below will be calculated by non-compartmental methods using WinNonlin professional or other appropriate software. AUC will be determined using lin-log trapezoidal rule. The variables AUC_{0-24} , C_{max} and t_{max} will also be calculated for AZ12555623, a metabolite of AZD1656. Other PK variables may also be calculated if judged appropriate.

AUC_{0-24} Area under the plasma concentration-time curve from time 0 to 24 hours post dose

C_{max} Observed maximum plasma concentration

t_{max} Time to reach C_{max}

$t_{1/2}$ Terminal half-life in plasma, calculated by $\ln 2/\lambda$ (λ is the elimination rate constant estimated from individual linear regression of the terminal part of the log concentration-time curve)

CL/F Oral clearance, calculated as dose/AUC_{0-24}

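### No PK sample is drawn before the Day 5 and Day 8 dose despite preceding bid dosing, so residual AZD1656 and metabolite at time 0 are not measured directly; the gap matters mainly for the metabolite

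*Protocol*

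**What the plan says.** Table 2 (Day 5 and Day 8) marks the pre-dose row as "Pre-dose | X | X | X | X | | Start telemetry". The empty cell is the PK column. PK samples 1 to 8 follow at 15 and 30 min and at 1, 1.5, 2, 4, 12 and 24 h. Footnote h of Table 1 describes the sampling in the same sense ("PK, PD and CR blood sampling will be done repeatedly during the 24-hour period after dose"), and the blood-volume table in Section 8.1 counts "1.2 | 8x2=16 | 19.2" for PK.

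Subjects are not drug-free at that point. Before Day 5, Section 4.1 has two titration days on bid dosing, then: "Thereafter the tolerated dose, 40 or 80 mg bid, will be maintained for two more days". Before Day 8 come two recovery days, "where AZD1656 will be maintained at the same dose bid as Day 3-4". Table 3 puts the second daily dose 9 h after the first ("Adm of IP followed by dinner").

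Section 12.3 defines AUC0-24 from time 0 and CL/F as dose over AUC0-24. AUC0-24, Cmax and tmax are also derived for the metabolite AZ12555623. Section 2.1 gives AZD1656 a half-life of about 3-4 h. For the metabolite it says the early decline runs parallel to the parent, but that "a slower terminal elimination phase is evident", with no figure.

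**The concern.** Starting at 15 min with no pre-dose tube suits a single dose in untreated subjects. Here a non-zero level is expected at time 0, and the 15 min sample already contains the new dose. No scheduled sample therefore shows directly how much of the observed AUC0-24 and Cmax belongs to earlier doses. Section 12.3 has no rule for a time-zero level that is present but unsampled. Its early-sample rule ("plasma concentrations below LLOQ will be taken as zero in the calculations") concerns measured samples before Cmax.

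At stake is the interpretation of the PK results, a secondary and descriptive objective, and above all those of the active metabolite. A later analysis plan can choose a formula, but it cannot supply a sample that was never drawn.

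**Working it through.** **1. Is the empty cell real?** Table 2 has 8 PK entries per clamp day: 8 x 2 = 16 samples, and 16 x 1.2 mL = 19.2 mL, as in Table 4. All Table 4 rows add up to the stated total: 5 + 21 + 21 + 19.2 + 2 + 3.5 + 7 + 3.6 + 18 + 22.5 + 336 + 9 = 467.8 mL. The same table counts 12 x 2 hormone samples, and Table 2 reaches 12 only with the pre-dose draw included. So the pre-dose draw is counted for hormones and not for PK. Footnote h alone would not settle this, because it also covers the hormone samples.

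**2. Time since the last dose.** 24 h - 9 h = 15 h, if morning doses are given at the same clock time each day.

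**3. AZD1656, by hand.** 15 h is 5 half-lives at 3 h and 3.75 at 4 h, so 3.1% to 7.4% of the evening dose remains. That dose is half the clamp-day dose. With linear kinetics and immediate absorption, earlier doses at 15, 24, 39, 48 h and so on leave, relative to the clamp-day dose, R = 0.5 x sum of 2^(-t/half-life). At 4 h:

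0.5 x (0.0743 + 0.0156 + 0.0012 + 0.0002) = 0.0457

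The share of AUC0-24 is R/(1+R) = 0.0457/1.0457 = 4.4%. The same formula gives 1.7% at 3 h and 2.9% at 3.5 h.

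**4. AZD1656, with absorption.** One-compartment superposition, tmax 0.5 to 1 h, 40 mg bid on Day 1, then 80 mg bid, and 160 mg as the single dose:

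- Carry-over relative to the dose's own AUC0-24 is 1.8% to 4.9%. As a share of the observed AUC0-24 this is 0.018/1.018 = 1.8% to 0.049/1.049 = 4.6%. Cmax is raised by the same 1.8% to 4.9%.
- The tail lost after 24 h is 0.4% to 1.7% of the single-dose AUC to infinity. Observed AUC0-24 therefore exceeds that AUC by 1.4% to 3.1%, and CL/F is about 1% to 3% low.

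**5. Metabolite.** The half-life is not in the protocol, so these values are assumptions. Each is treated as governing the whole profile, which overstates carry-over because the early decline follows the parent.

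| Assumed half-life | Carry-over / own AUC0-24 | Share of observed AUC0-24 |
|---|---|---|
| 6 h | 0.132 | 0.132/1.132 = 12% |
| 8 h | 0.233 | 0.233/1.233 = 19% |
| 12 h | 0.451 | 0.451/1.451 = 31% |

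Under this model Cmax is inflated in the same proportion.

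**6. Day 5 against Day 8.** Modelled carry-over is the same on both days for the parent. It differs by at most 0.1 percentage points of own AUC for the metabolite at 6 to 12 h (0.4505 against 0.4495 at 12 h).

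**The case against.** The strongest case against is that the residue can be recovered without the tube. The clamp-day dose equals the previous total daily dose and no evening dose follows, so the time-zero level is roughly half of (C15 + C24), with C15 log-interpolated between the 12 h and 24 h samples. Under linear kinetics and no food effect this is within about 3% for AZD1656 and about 12% for the assumed metabolite profiles. Dosing is supervised and recorded. This stands, so a reader who infers that the carry-over cannot be removed goes too far. But the approximation needs a 24 h value above the 5 nmol/L LLOQ. It also rests on linearity between doses taken with food and a fasting dose, which a trough would check.

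Second, entering the tube merely as the time-zero value hardly changes AUC0-24: at most about 0.1% for the parent and 0.3% for the metabolite scenarios. That also stands. The value of the tube lies in measuring the residue, not in the first trapezoid.

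Third, CL/F is derived only for AZD1656, and there carry-over partly replaces the lost tail. Metabolite exposure is about 20% of the parent's (Section 2.1). Both limit the weight of the point.

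Two further inferences are tempting and not supported. One is that the missing trough undermines the comparability of the two clamp periods claimed in Section 4.2. That claim rests on giving the same bid dose before each, and the modelled carry-over is practically equal on both days. The other is that the jump from 4 h to 12 h seriously damages AUC0-24. With the lin-log rule the scheduled samples reproduce it within about 1% for the parent and 1.5% for the metabolite scenarios.

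**Conclusion.** The point holds in a limited form. No PK sample precedes the Day 5 and Day 8 dose although earlier doses have left some residue, so that residue is approximated rather than measured.

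- **AZD1656:** small, about 2-5% of AUC0-24 at the protocol's own half-life.
- **Metabolite:** not fixed by the protocol. About 12%, 19% and 31% are upper bounds for assumed half-lives of 6, 8 and 12 h.

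Drug and metabolite should not be put on the same footing. All figures assume linear kinetics, no food effect and a 15 h interval. The primary glucose comparison is not touched. This is a low-cost improvement to a secondary, descriptive objective. It is worth making before dosing starts, because the sample cannot be obtained afterwards.

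**What to change.** - In Table 2, add a PK tube to the existing pre-dose draw on Day 5 and Day 8, and adjust footnote h of Table 1.
- Report the result as a trough for AZD1656 and AZ12555623 on both days.
- In Section 12.3, state that it is the time-zero value for AUC0-24 and is used to quantify the carry-over in AUC0-24 and Cmax, mainly for the metabolite.
- In Table 4, change PK to 9 x 2 = 18 samples: 18 x 1.2 = 21.6 mL, total 467.8 + 2.4 = 470.2 mL.

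The cost is 2.4 mL more blood and two more PK samples to assay per subject, with no new venepuncture. A PK tube at the existing 6 h draw is optional and not needed for this point.
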